Title: Circuitry-Guided Smoking Cessation in Schizophrenia

Grant number: UG3DA047685

NCT number: NCT03281629

Document date: 02/01/2022

PIs: [name], PHD; L. [name] (contact)

Study protocol

Background

The prevalence of cigarette smoking in schizophrenia patients (45%-65%) is 3-5 folds higher(Lasser et al., 2000) than the smoking rate (~14%) in the general U.S. population. Although smoking rate has declined in persons with mental illness(Han et al., 2022), the quit rate is low in the schizophrenia population(Lasser et al., 2000; Aubin et al., 2012). Identifying the neurobiological bases responsible for such high smoking vulnerability and continued use is critical to devise better intervention strategies to reduce cigarettes smoking in individuals with schizophrenia.

Many brain regions such as medial/lateral prefrontal cortex, cingulate, insula, ventral striatum, hippocampus, thalamus, and amygdala (Loughead et al., 2010; Franklin et al., 2011; Franklin et al., 2012; Menossi et al., 2013; Funk et al., 2016; Joutsa et al., 2022) and functional connectivity involving anterior cingulate, striatum and insula, medial prefrontal, and temporal cortices regions (Hong et al., 2009; Li et al., 2017; Hsu et al., 2019; Keeley et al., 2020) have been implicated in nicotine addiction. Evidence from animal studies has suggested that the basolateral amygdala, which has bi-directional neural connections with prefrontal cortex and hippocampus, is associated with nicotine addiction(Sharp, 2019). Importantly, many of these structures, especially the amygdala and prefrontal cortex, are also closely associated with schizophrenia(Ho et al., 2019; Zheng et al., 2019; Guimond et al., 2021). Direct comparisons between nicotine addiction and schizophrenia showed shared abnormal functional connectivity between the dorsal anterior cingulate cortex and bilateral subcortical extended amygdala(Moran et al., 2013). The

extended amygdala mainly describes a neuroanatomic region with dense cholinergic neurons, centered at the nucleus basalis and the surrounding structures including the amygdala, substantia innominata, hippocampus, and ventral striatum. It is also the region with the highest nicotine binding in the brain(Shimohama et al., 1985; Cairns et al., 1988; Heimer, 2003). The cholinergic projections from the extended amygdala reach essentially the entire cortex and are important for attention and arousal(Sarter et al., 1999; Heimer, 2003). The extended amygdala may be at the center of the cortical-subcortical reentrant pathways critical for understanding and treating addiction and schizophrenia(Leshner et al., 1999; Heimer, 2000; 2003).

We hypothesized that neuromodulation of the extended amygdala area, a region likely contributing to both nicotine addiction and schizophrenia pathophysiology, may help in correcting the nicotine addiction - schizophrenia comorbidity. However, there is currently no noninvasive method that can specifically target this area, making it difficult to directly test the hypothesis.

Conventional neuromodulation approaches such as repetitive transcranial magnetic stimulation (rTMS) can only stimulate neurons at the scalp surface, while the H-coil method can stimulate deeper but more diffuse brain areas. Previous H-coil neuromodulation was found to be efficacious for short-term smoking cessation(Dinur-Klein et al., 2014; Zangen et al., 2021), although even this approach cannot stimulate deeply enough to reach the extended amygdala. Moreover, rTMS over dorsolateral prefrontal cortex for treating cigarettes use(Eichhammer et al., 2003; Amiaz et al., 2009; Li et al., 2020)and craving(Amiaz et al., 2009; Rose et al., 2011; Hayashi et al., 2013; Li et al., 2013; Trojak et al., 2015; Chang et al., 2018; Li et al.,

2020) resulted in mixed findings (Wing et al., 2012; Prikryl et al., 2014). Identifying alternative circuitry abnormalities that maybe more causally linked to smoking in schizophrenia may be needed in our effort to develop more effective treatment strategy for nicotine addiction in this patient population.

In our pilot study, we identified TMS-targetable cortical brain regions that have robust functional connectivity with the extended amygdala that are related to nicotine addiction. We proposed to use rTMS to test whether modulating this circuit is associated with changes in smoking behaviors in smokers with schizophrenia.

Materials and methods

Participants

We examined whether the nicotine addiction related circuitries thus identified could be modulated by TMS and produce a reduction in nicotine addiction. We used a 20-TMS-session, sham-controlled, parallel-group, participant- and rater-blinded, randomized study design to test this hypothesis. The TMS cortical target that satisfied the pre-defined criteria in our pilot study was the dorsomedial prefrontal cortex (-15, 28, 48 in Talairach space. Details in Results). For this study, 30 SSD smokers (cigarettes per day ≥ 5 over the past 4 weeks) were enrolled.

Participants were randomly assigned to receive active or sham TMS at a 2:1 ratio, which allows for more statistical power in the TMS group to explore the association between changes of rsFC and changes of addiction severity. Of the 30 randomized, 26 completed, including 16 in the TMS and 10 in the sham group. The 2:1 ratio of randomization was chosen to assure more statistical power in the TMS group for exploring the association between changes of rsFC and changes of

nicotine addiction severity. Conditions including major medical and neurological illnesses, history of head injury with cognitive sequelae, mental retardation, substance dependence within the past 6 months or current substance abuse (except nicotine), and pregnancy were exclusionary. Subjects were asked not to consume caffeinated drinks prior to scan and be abstinent from alcohol for 24 hours prior to each fMRI and TMS session. No participant vaped or used electronic cigarettes before or during the treatment. Pregnant females were excluded. SSD smokers were not required to be smoking cessation treatment-seeking as the primary purpose here was to assess target engagement, i.e., whether TMS can impact the nicotine addiction severity-related circuitries and such effects, if found, would be related to change in nicotine addiction severity.

TMS

There were 20 TMS sessions over ~4 weeks. Stimulations were 10Hz pulse trains that are considered facilitatory(Wassermann, 1998), delivered as a 4-second stimulation train, followed by a 26-second quiet period, for a total of 30 trains lasting ~15 minutes (1,200 pulses per session). The 10Hz stimulation was selected based on findings from our pilot study that more severe FTND was correlated with lower rsFC (see Results) and accordingly, we hypothesized that facilitatory TMS may induce an increase of the rsFC and reduce nicotine addiction severity. The TMS target was the rsFC-defined dorsomedial prefrontal cortex (details in Results). The Brainsight™ Navigation system (Rogue Research Inc) was used to precisely stimulate the target throughout the treatment. A Magstim Super Rapid² Plus1 stimulator and two Magstim air-film, figure-of-eight, 70-mm coils (one active and one sham) were used. The sham coil provided controls for appearance, procedure, and auditory related confounds but not the TMS skin

sensation. Therefore, we combined the sham coil with electric current stimulation (Coulbourn E13-22) and large area electrodes (EPAD, Thymapads) to generate similar skin sensations (Borckardt et al., 2008) at the forehead, triggered by TMS pulses. The pads were also applied to the active TMS condition but without electric stimulation. Participants were asked to guess their group assignment at the end.

We used individualized electric field modeling through SimNIBS (Thielscher et al., 2015) to define both the TMS intensity and coil orientation (Stokes et al., 2007; Deng et al., 2013; Stokes et al., 2013). The individualized TMS intensity was determined to induce electric field strength of 100 V/m or above to ensure effective and comparable stimulations across participants. The TMS coil was positioned so the induced currents ran perpendicular to the gyral orientation of the dorsomedial prefrontal site (Opitz et al., 2011).

Clinical and smoking related assessments

Cigarettes per day and urine cotinine were the primary tobacco consumption indices and the FTND was used to represent severity of nicotine addiction. Previous factor analyses showed that the primary factor of the FTND was loaded with item 1, 3, and 5 of the six FTND questions, which asked time to first cigarette in the morning, whether the first cigarette in the morning or the rest of the cigarettes is most preferred, and whether one smokes more frequently in the first hour of the morning. These are symptoms representing severity of morning withdrawal symptoms or difficulty to maintain abstinence after overnight nonsmoking (Radzius et al., 2003). We used the sum of these items to refer to ‘morning smoking severity’ of the FTND. FTND score and cigarettes per day were obtained at baseline, session 5 (treatment week 1), 10 (week 2),

15 (week 3), and 20 (week 4). Imaging was performed at baseline, session 5, 10, and 20. The Brief Psychiatric Rating Scale (BPRS) measured the overall psychiatric symptoms(Hedlund et al., 1980). BPRS and urine cotinine were measured at baseline and session 20. All participants (whether receiving active or sham TMS) were encouraged to quit smoking using a standard psychoeducational clinical procedure. Staff conducting these procedures and assessments were blinded to group assignment.

Imaging data acquisition and analysis

Resting-state fMRI scans were obtained using a 3T Siemens Prisma scanner equipped with a 64-channel head coil. The Human Connectome Project multi-band sequences were used: echo-planar pulse sequence with 2mm isotropic, TR=720ms, MB=8, AP/PA encoding, 4 runs \times 5.4 min each=24minutes). High-resolution (0.8 \times 0.8 \times 0.8mm³) T1-weighted MPRAGE images were acquired. Data were processed using Analysis of Functional NeuroImages (AFNI)(Cox, 1996) software. The preprocessed data were spatially smoothed to a FWHM of 6 mm. The linear trend, 6 motion parameters, their 6 temporal derivatives and time courses from the white matter and cerebral spinal fluid were removed as regressors of no interest. Time points with excessive motion (>0.3mm) and their neighboring time points were censored. Images were spatially normalized to the Talairach space(Talairach et al., 1988). Individual statistical maps were then calculated using a seed-based correlation analysis using dorsomedial prefrontal cortex as seed. The mean time-series within each seed ROI was correlated with the time course of each voxel in the brain to obtain resting-state functional connectivity (rsFC). Pearson's correlation coefficients were converted to z values using Fisher's r-to-z transform.

Statistical Analysis Plan

Demographics were compared using ANOVA or χ^2 tests. Target engagement was evaluated by extracting dorsomedial prefrontal cortex seeded rsFC with the extended amygdala regions, including bilateral hippocampus, amygdala, and substantia innominate. The linear mixed effect model was used to evaluate the group by time interaction of rsFC on FTND, cigarettes per day, and urine cotinine, although statistical significance using this full model was not expected as this was a proof-of-concept study. Exploratory analyses were conducted comparing TMS vs. sham at different time points using independent-sample t-test and comparing baseline vs. post-TMS measurements using paired-sample t-tests at $p < 0.05$. Effect sizes were calculated for nominally significant measures using Cohen's d . The primary analyses assessed the strength of the associations between changes of rsFC and changes in the smoking measures, using Spearman's correlation to account for non-normal distributions. All tests were two-tailed.

References

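### Four of 30 randomised participants did not complete, possibly all on TMS, and the session-20 tests and change correlations omit anyone without that visit; a mixed model on all 30 should supply the estimates

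*Combined protocol and SAP*

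**What the plan says.** On allocation and completion, the Participants section under Materials and methods states: "Participants were randomly assigned to receive active or sham TMS at a 2:1 ratio", and then: "Of the 30 randomized, 26 completed, including 16 in the TMS and 10 in the sham group". It does not give the number randomised to each arm, whether randomisation was blocked, or the arm, timing or reason of each loss.

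Clinical and smoking related assessments sets the visits. FTND and cigarettes per day are taken at baseline and sessions 5, 10, 15 and 20. Imaging is at baseline and sessions 5, 10 and 20. Urine cotinine is taken only at baseline and session 20.

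The Statistical Analysis Plan lists four kinds of analysis:

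- Mixed model: "The linear mixed effect model was used to evaluate the group by time interaction of rsFC on FTND, cigarettes per day, and urine cotinine". The plan adds that significance from this model was not expected.
- Between-arm tests: "Exploratory analyses were conducted comparing TMS vs. sham at different time points using independent-sample t-test".
- Within-person tests: "comparing baseline vs. post-TMS measurements using paired-sample t-tests", at the 0.05 level, with Cohen's d for nominally significant measures.
- Primary analysis: "The primary analyses assessed the strength of the associations between changes of rsFC and changes in the smoking measures, using Spearman's correlation".

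No analysis population, missing-data method or sensitivity analysis is stated.

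**The concern.** Four of 30 (13%) of those randomised have no stated place in the analysis. An independent-sample t-test at a visit needs that visit's value. A paired test or a change score needs both baseline and the later visit. So the between-arm and within-arm results at the end of treatment, and the effect sizes built on them, come from people who reached session 20. Cotinine is one of the two primary tobacco consumption indices and has no interim measurement, so someone without session 20 contributes no cotinine change at all.

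If the people who left would have changed differently from those who stayed, the end-of-treatment TMS change no longer describes the arm as randomised. The correlation between connectivity change and smoking change then describes a selected subset. The 2:1 ratio was chosen to strengthen that correlation in the TMS arm, so losses there fall where the design most wanted numbers. Of the methods listed, only the mixed model can keep partial follow-up, and the plan does not say that it is fitted to everyone randomised.

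**Working it through.** **Inputs.** 30 randomised, 2:1 ratio, 16 TMS and 10 sham completers (Participants); visit schedule (Clinical and smoking related assessments); methods (Statistical Analysis Plan).

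**1. The plan's own figures.** 16 + 10 = 26, as stated. Losses: 30 − 26 = 4.

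**2. Losses by arm.** An exact 2:1 split is 30 × 2/3 = 20 TMS and 10 sham. Losses are then 20 − 16 = 4 and 10 − 10 = 0, that is 20% (95% CI 5.7% to 43.7%) v 0% (upper limit 30.8%). Five splits are compatible with 16 and 10 completers. The last two columns assume that non-completers had zero change. The completer mean then exceeds the all-randomised mean by (number randomised ÷ completers) − 1 in each arm.

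| Split TMS:sham | Lost TMS:sham | Loss rates | Fisher p | TMS mean too large by | Sham mean too large by |
|---|---|---|---|---|---|
| 20:10 | 4:0 | 20.0% v 0% | 0.27 | 20/16 − 1 = 25% | 10/10 − 1 = 0% |
| 19:11 | 3:1 | 15.8% v 9.1% | 1.0 | 19/16 − 1 = 18.75% | 11/10 − 1 = 10% |
| 18:12 | 2:2 | 11.1% v 16.7% | 1.0 | 18/16 − 1 = 12.5% | 12/10 − 1 = 20% |
| 17:13 | 1:3 | 5.9% v 23.1% | 0.29 | 17/16 − 1 = 6.25% | 13/10 − 1 = 30% |
| 16:14 | 0:4 | 0% v 28.6% | 0.037 | 16/16 − 1 = 0% | 14/10 − 1 = 40% |

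Only 20:10 matches the stated ratio exactly. Under it, with equal risk of loss in both arms, the chance that all four losses fall on TMS is C(20,4)/C(30,4) = 4845/27405 = 0.18.

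If allocation was simple rather than blocked, and loss did not depend on arm, each lost participant was on TMS with probability 2/3. Then 4:0 has probability (2/3)^4 = 16/81 = 0.20, 3:1 has 32/81 = 0.40 and 2:2 has 24/81 = 0.30.

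**3. Bias when non-completers differ from completers.** Under 20:10, completer mean minus all-randomised mean = (4/20) × (completer mean minus non-completer mean). If non-completers would have done 0.5 to 1.0 SD worse, the TMS mean is too favourable by 0.2 × 0.5 = 0.10 to 0.2 × 1.0 = 0.20 SD. If they would have done better by the same amounts, it is too unfavourable by 0.10 to 0.20 SD. The documents give no basis for choosing between these.

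**4. Precision under 20:10.** The between-arm variance ratio is (1/16 + 1/10)/(1/20 + 1/10) = 0.1625/0.15 = 1.083, or 8% higher. This is loss of information, not bias.

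**5. Which analyses are exposed.** Someone who left after session 5 or 10 can still enter the t-tests and change correlations at the visits attended. Session-20 tests, session-20 change correlations and every cotinine change exclude anyone without session 20. The mixed model can use partial follow-up for FTND and cigarettes per day. It can do the same for rsFC if rsFC is fitted as an outcome.

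**The case against.** Four objections have force.

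- **A reader might infer that the t-tests and correlations are restricted to completers by construction, so that early data are wasted.** The documents do not support this. The plan tests TMS against sham at several time points, each test needs only that visit's value, and nothing limits any analysis to the 26. The accurate description is available cases at each visit, with the analysis set undefined. The point still stands for session 20 and for cotinine.
- **A reader might take the mixed model as having been set aside.** It was not. The plan says it was used, and only its statistical significance was not expected. What is missing is a statement that it includes all 30, and its use as the source of the estimates.
- **A reader might conclude that TMS drove people out, or that the TMS effect is inflated.** Neither follows. The 4:0 pattern is inferred, Fisher p = 0.27 does not show differential loss (though ten sham participants cannot exclude it), and no reasons for loss are given. The bias could be nil or reversed.
- **The 25% concerns a mean change, whereas the primary analysis is a rank correlation.** This is correct. The percentage does not carry over to the correlation, which selective loss could raise or lower. The mean changes belong to tests that the plan calls exploratory, in a proof-of-concept study.

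These points limit the claim but do not supply a missing-data rule, and they do not make session-specific t-tests preferable to a model that keeps everyone.

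**Conclusion.** The concern holds in a limited form. Four of 30 did not complete. If allocation was exactly 20:10, all four were on TMS. Session-20 comparisons and all cotinine changes leave out anyone without that visit, and the plan does not say how this is handled. The TMS-arm change and the correlation between rsFC change and smoking change can each be biased in either direction.

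The one-directional figure, a TMS mean change 0% to 25% too large, rests on two assumptions: that non-completers had no change, and that they lack session-20 data, since completion is not defined. Its upper end also needs the 20:10 split. It illustrates possible size and is not an estimate of actual bias. The change is worth making because it is cheap and needs no new data. It does not overturn the study's conclusions.

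**What to change.** 1. Take the between-arm and within-arm estimates and effect sizes for FTND, cigarettes per day and rsFC from the mixed model, fitted to all 30 randomised participants with every available session, instead of from session-specific and paired t-tests. Fit rsFC as an outcome in its own right, since the current wording does not clearly do so. State the missing-at-random assumption; the model does not recover unseen session-20 values.
2. For session-20 results, including cotinine, add a sensitivity analysis with non-completers set to no change from baseline. Label it an assumption and not a best estimate: it treats imputed values as observed, and under 20:10 it alters only the TMS arm.
3. Describe the session-20 change correlations as conditional on having that visit.
4. In support, give numbers randomised, lost and analysed by arm, with the timing and reason of each loss.

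The cost is SAP wording and a few extra model runs. The estimated effect may be slightly less favourable.

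### Effect sizes are planned only for t-tests that reach p<0.05, in an uncounted and unadjusted set, while the comparison with sham has no rule for reporting or reading it

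*Combined protocol and SAP*

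**What the plan says.** The Participants section gives the purpose as target engagement: "whether TMS can impact the nicotine addiction severity-related circuitries and such effects, if found, would be related to change in nicotine addiction severity". The Statistical Analysis Plan section offers three kinds of analysis that bear on this.

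- **Mixed model.** Its target is the "group by time interaction of rsFC on FTND, cigarettes per day, and urine cotinine". In the same sentence the plan qualifies what it hopes to see from this model: "although statistical significance using this full model was not expected as this was a proof-of-concept study".
- **t-tests.** One family sets the two arms against each other: "Exploratory analyses were conducted comparing TMS vs. sham at different time points using independent-sample t-test". The other looks at change within an arm, with no use of the sham group: "comparing baseline vs. post-TMS measurements using paired-sample t-tests at $p < 0.05". I read the threshold as covering both families. Outcomes, visits, regions and (for the paired tests) arms are not listed. There is no multiplicity statement. Cohen's d is to be calculated for measures that reach nominal significance.
- **Spearman correlations** of change in rsFC with change in smoking, which the plan names as primary.

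Nothing says which estimates are reported from the mixed model, or how a nominally significant t-test is read beside a null interaction.

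**The concern.** The primary correlations relate change to change and, as written, do not compare arms. Whether TMS rather than time or quit advice moved the circuit or smoking can be answered only through the sham arm, that is, by the mixed model or the between-arm t-tests. The plan lowers expectations of the first and attaches its only effect-size rule to p<0.05 results.

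Three things follow. Some nominal result is fairly likely by chance alone. The effect sizes that reach the report are those that passed a significance filter in a small sample, so they are too large on average. And a within-arm paired result can be significant with no TMS effect, because the Clinical and smoking related assessments section says that participants in both arms were encouraged to quit.

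**Working it through.** The plan gives no test count, power or family-wise error rate, so there is no stated figure to reproduce.

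**Inputs from the document**
- 16 TMS and 10 sham completers (Participants).
- FTND and cigarettes per day at 4 post-baseline visits, urine cotinine at 1, imaging at 3 (Clinical and smoking related assessments; imaging is at sessions 5, 10 and 20).
- Hippocampus, amygdala and substantia innominata as rsFC regions: read as 1 composite, 3 regions, or 6 if each side counts.
- Each test at 0.05; "All tests were two-tailed".

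**Assumed, because the document gives no values**
- Central case: correlation 0.8 across smoking visits, 0.6 across rsFC visits, 0.5 between smoking measures, 0.6 between regions.
- Range: 0.5 to 0.9 across smoking visits, 0.4 to 0.7 across rsFC visits, 0.2 to 0.6 between smoking measures, 0.3 to 0.7 between regions.

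**Count of tests**
- Between-arm: 4 + 4 + 1 = 9 smoking tests, plus 3 per rsFC measure, giving 12, 18 or 27.
- Paired, TMS arm, session 20 only: 3 + 1, 3 + 3 or 3 + 6 = 4, 6 or 9. Totals 16, 24, 36.
- Paired at every visit: 12, 18 or 27 again. Totals 24, 36, 54.

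**Chance of at least one p<0.05 with no TMS effect and no time trend.** For independent tests it is 1 - 0.95^m. For correlated tests it comes from simulated normal data with the actual t-tests at 16 v 10 (simulation error one to two points).

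| rsFC measures | Paired tests at | Tests | Independent | Central case | Range |
|---|---|---|---|---|---|
| 1 | session 20 | 16 | 56% | 43% | 40-53% |
| 1 | all visits | 24 | 71% | 58% | 55-64% |
| 3 | session 20 | 24 | 71% | 57% | 51-67% |
| 3 | all visits | 36 | 84% | 71% | 69-78% |
| 6 | session 20 | 36 | 84% | 69% | 59-79% |
| 6 | all visits | 54 | 94% | 80% | 76-90% |

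Between-arm tests alone give about 32% (12 tests) to 55% (27 tests) in the central case. If rsFC is left out, the 9 between-arm smoking tests give 19-32%, and the 12-test set that adds paired tests at session 20 gives 30-43%.

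**Common improvement.** If both arms improve by an assumed 0.25 SD with no TMS effect, the 16-test figure rises to 66-84%. The rise comes from the paired tests.

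**Selection on p<0.05.** A between-arm t-test has t = d / sqrt(1/16 + 1/10) on 24 df. Significance needs |d| of at least 2.064 x 0.4031 = 0.83. Power at 16 v 10 (noncentral t) is 22% for a true 0.5 SD and 48% for 0.8 SD; 80% power needs 1.18 SD. So a true effect of 0.5 SD would pass the filter about one time in five, and its reported size would then be at least 0.83 / 0.5 = 1.66 times the truth. This holds where the between-arm test does the selecting. The plan speaks of significant measures, so a measure selected by its paired test might also be given a d.

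**The case against.** The strongest reply is that the plan is modest about these tests. It calls them exploratory, calls their hits nominal, and makes the correlations primary. The remark about the model is a fair statement of low power, which the 22% and 48% above support. All of that stands and lowers the weight of the point. It does not say what conclusion the tests may support, and it does not remove the filter on effect sizes.

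The counts are also mine. Paired tests at session 20 only is a natural reading, and with one rsFC composite it puts the central chance below one half. The higher figures depend on more regions, more visits, and counting both families of tests.

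Three stronger readings are tempting and are not supported:
- A reader might infer a rule that a null model is set aside and any t-test hit is taken as a signal. No such rule is written; the plan is silent on the reading.
- A reader might infer that the null was excused before the data were seen. The text is in the past tense and already reports completers, so the sentence cannot be dated.
- A reader might infer that the t-tests cannot tell an effect from none. They can. For the 16-test set, at least one hit occurs in 39-51% of null runs and in 98-100% with an assumed 0.5 SD effect on every measure; for the 12 between-arm tests alone, 28-41% v 70-86%. A set with no hits would be informative. The fault is an inflated false-positive rate, not an absence of information.

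**Conclusion.** The point holds as a fault of reporting and interpretation in the secondary analyses. Under no effect, a nominal result somewhere is roughly an even chance or better on most readings that include rsFC, and somewhat below that on the narrowest. These figures rest on assumed correlations, on completers only, and on the reading of which tests are run. The 0.83 threshold needs none of the assumed correlations: it follows from 16 v 10 and p<0.05 alone, and it is the firmest part.

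The mixed model as worded does not settle the matter. It names the smoking measures where the outcomes would stand and treats rsFC as a term, so a model with rsFC as the outcome, which target engagement requires, is not clearly specified.

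**What to change.** 1. Specify the mixed model with each rsFC measure and each smoking measure as an outcome. Report the group-by-time (between-arm change) estimate with its 95% CI for every measure, whatever its p-value. This replaces the rule that limits effect sizes to nominally significant measures. Where an interval includes zero, state that an effect was not shown and give the range not excluded.
2. State that the visit-wise and paired t-tests are descriptive, that within-arm change is not evidence of a TMS effect, and that an isolated p<0.05 cannot support a statement that TMS engaged the circuit or changed smoking.
3. Report how many measures and tests were examined, and note that the model intervals are themselves unadjusted. With 3 smoking and 1 to 6 rsFC measures, and one estimate each, there are 4 to 9 intervals. If independent, the chance that at least one wrongly excludes zero is 1 - 0.95^4 = 19% to 1 - 0.95^9 = 37%.

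A permutation correction over the paired tests would not help: flipping signs within an arm tests for change over time, not for a TMS effect.

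The cost is SAP wording and a fuller table from data already collected. The downside is that an isolated nominal result can no longer be presented as a signal.

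### The exploratory TMS v sham t-tests name no baseline adjustment and the paired tests make no contrast with sham; add baseline-adjusted differences with 95% CIs at each visit

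*Combined protocol and SAP*

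**What the plan says.** The Statistical Analysis Plan section lists these analyses:

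- **Primary:** "The primary analyses assessed the strength of the associations between changes of rsFC and changes in the smoking measures", by Spearman's method, chosen as a "correlation to account for non-normal distributions". This is an association between changes, not an arm comparison.
- **Mixed model:** "The linear mixed effect model was used to evaluate the group by time interaction". The plan does not expect significance from it. It does not say how baseline enters or which visit contrasts are reported.
- **Exploratory tests:** "comparing TMS vs. sham at different time points using independent-sample t-test and comparing baseline vs. post-TMS measurements using paired-sample t-tests", each at two-sided p<0.05. No baseline term is named, and the plan does not say whether the arm comparison uses raw or change values.
- **Effect sizes:** "Effect sizes were calculated for nominally significant measures", using Cohen's d. No confidence interval is named.

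On design, the Participants section states: "Participants were randomly assigned to receive active or sham TMS at a 2:1 ratio". On completion it states: "Of the 30 randomized, 26 completed, including 16 in the TMS and 10 in the sham group".

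Under Clinical and smoking related assessments, FTND and cigarettes per day are recorded at baseline and sessions 5, 10, 15 and 20; imaging at baseline and sessions 5, 10 and 20; cotinine at baseline and session 20. Both arms received the same encouragement to stop smoking.

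**The concern.** Because the primary analysis does not compare arms, the evidence from the randomisation rests on the exploratory t-tests and the mixed model. Four features weaken it.

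1. An unadjusted t-test keeps its type I error rate but discards baseline information already collected. With arms this small, chance imbalance at baseline is common and carries through to the raw follow-up difference.
2. A paired test measures change within an arm. Since both arms were encouraged to quit, a shared change is plausible, and a paired result in the TMS arm cannot separate it from a TMS effect. If paired tests are run in both arms and compared, the larger arm reaches p<0.05 more often even when both change equally.
3. Effect sizes shown only after significance leave no estimate for the other measures and overstate those that pass. This matters for a proof-of-concept study whose estimates may feed a later trial.
4. Four of the 30 randomised did not complete. A completer comparison may be biased, with or without adjustment.

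**Working it through.** The plan states no power, precision or sample-size figure, so there is none to reproduce.

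**Inputs.** From the documents: 16 v 10 completers (16 + 10 = 26), two-sided 0.05. Assumed: normal data with SD = 1, true differences of 0.8 or 0.5 SD, and a baseline-to-follow-up correlation r, shown over a range.

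**Precision and power.** SE = √(1/16 + 1/10) = 0.403 SD.

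- Raw t-test: half-width = t(0.975, 24) × 0.403 = 2.064 × 0.403 = 0.83 SD.
- Change-score t-test: variance factor 2(1−r), 24 df.
- ANCOVA: variance factor (1−r²)(1 + 1/22), 23 df.

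Power comes from the noncentral t distribution.

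| r | 95% half-width: change / ANCOVA (SD) | Power at 0.8 SD: raw / change / ANCOVA | Power at 0.5 SD: raw / change / ANCOVA |
|---|---|---|---|
| 0.3 | 0.98 / 0.81 | 47.8 / 36.3 / 49.6% | 22.2 / 17.2 / 23.0% |
| 0.5 | 0.83 / 0.74 | 47.8 / 47.8 / 57.4% | 22.2 / 22.2 / 26.9% |
| 0.7 | 0.64 / 0.61 | 47.8 / 69.1 / 74.0% | 22.2 / 33.7 / 37.0% |
| 0.8 | 0.53 / 0.51 | 47.8 / 85.3 / 87.2% | 22.2 / 46.9 / 49.1% |

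At r = 0, ANCOVA has half-width 0.85 SD and power 46.0% and 21.4%, a loss of about 2 and 1 points against raw. It breaks even with the raw test at r of about 0.22. Simulation of the ANCOVA powers, 100,000 trials per cell, agreed within 0.3 points.

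**Baseline imbalance.** P(|imbalance| > 0.5 SD) = 2[1 − Φ(0.5/0.403)], about 21%. In 20,000 simulated trials with no TMS effect and r = 0.7, those with imbalance above +0.5 SD gave a mean difference of 0.49 SD unadjusted and 0.00 SD adjusted.

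**Skewed cigarette counts.** Entry required "cigarettes per day ≥ 5 over the past 4 weeks". The assumed model was a lognormal baseline (median 15, log-SD 0.5, truncated at 5), follow-up median 12, TMS follow-up 40% lower, and log-scale correlation 0.3/0.5/0.7/0.8.

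- No zeros: power 66/67/68/68% raw v 68/75/88/95% ANCOVA.
- 10% zeros in both arms: 48/49/49/49% v 49/52/60/66%.
- Type I error was 4.6–4.9% for both methods. With 10% zeros, ANCOVA on log(x+1) fell to 29–36% power.

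**Paired tests.** Assume no TMS effect and the same standardised change dz in both arms. With p16 and p10 the chances of significance in 16 and 10 people, P(TMS only) = p16(1 − p10) and P(sham only) = p10(1 − p16).

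- dz = 0.2: 0.116 × 0.912 = 11% v 0.088 × 0.884 = 8%.
- dz = 0.5: 0.465 × 0.707 = 33% v 0.293 × 0.535 = 16%.
- dz = 0.7: 0.745 × 0.494 = 37% v 0.506 × 0.255 = 13%.
- dz = 0: the two are equal.

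**Significance-filtered effect sizes.** The smallest between-arm d that reaches p<0.05 is 2.064 × 0.403 = 0.83. For a true d of 0.5, the mean reported |d| among significant results is 1.10 (400,000 trials).

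**Non-completers.** The number randomised per arm is not given. If 2:1 produced exactly 20:10 (an assumption), all four losses were in the TMS arm. If those four would have differed from TMS completers by 0.5 or 1.0 SD, the TMS mean is off by (4/20) × 0.5 = 0.10 or (4/20) × 1.0 = 0.20 SD. ANCOVA removes only the part explained by baseline.

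**The case against.** No error is shown. The t-tests are valid, the comparisons are labelled exploratory, the stated purpose is target engagement, and the primary analysis is untouched. This stands, and it limits the weight of the point.

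The planned mixed model may already do much of the work: if baseline is one of its time points, the group-by-time contrast is a difference in change from baseline. That is fair, and the fix uses that model. But the plan's sentence speaks of the interaction of rsFC on the smoking measures, which leaves the outcome unclear, and it names neither baseline handling nor visit contrasts.

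The raw t-test is the comparator most favourable to ANCOVA. Against the better of raw and change scores at r = 0.3/0.5/0.7/0.8, the gain is about 2/10/5/2 points at 0.8 SD and 1/5/3/2 at 0.5 SD. This also stands. Yet no single t-test is best across that range, and under the normal model ANCOVA beats both readings over all of it.

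The plan does not say which arms had paired tests, that a paired result will be read as efficacy, or that analyses were restricted to completers. Those parts are therefore conditional.

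The fix yields 4 + 4 + 3 + 1 = 12 contrasts, more if connectivity is split by region, with no multiplicity control. The planned per-visit t-tests carry the same multiplicity. The intervals should be read as estimates.

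**Conclusion.** The concern holds as a recommended improvement to the exploratory analyses, with medium confidence. Nothing in the primary Spearman analysis changes.

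The size of the gain depends on r, which the documents do not give. It is appreciable against raw values when r is 0.5 or more, modest against change scores at high r, and slightly negative against raw values below about 0.22. Adjustment does not rescue the sample size: at a 0.5 SD difference, power stays under 50% up to r = 0.8.

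The effect-size point does not depend on r, though the average inflation depends on the assumed true effect. The paired-test asymmetry requires a shared change and tests in both arms. The non-completer figures rest on an assumed 20:10 split.

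**What to change.** - Make the main exploratory arm comparison the baseline-adjusted TMS-minus-sham difference with 95% CI: FTND and cigarettes per day at sessions 5, 10, 15 and 20; rsFC at 5, 10 and 20; cotinine at 20.
- Obtain it from the planned mixed model with baseline as a covariate, including any post-baseline visits of the four non-completers, or from ANCOVA.
- Keep the listed t-tests beside it and state whether they use raw or change values.
- Present paired within-arm changes as descriptive, not as evidence of a TMS effect.
- Report effect sizes with CIs for all measures, whatever the p-value.
- State that completer-only results may be biased by the four non-completers.
- Check with permutation p-values, since the plan itself cites non-normality. Use a log scale only for measures without zeros.

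The cost is SAP wording and some analysis time, with no new data. Adjustment uses one degree of freedom and loses up to about 2 points of power if baseline is uncorrelated with outcome. The document is written in the past tense and reports completion, so the adjusted analysis should be disclosed as added, and labelled post hoc if it is done after data were seen.
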